Available Immunogenicity Population: Available Immunogenicity Population will consist of all eligible randomized subjects who receive at least one vaccination, and have at least one post immunogenicity data determination. Available Immunogenicity Population will also be used to the immunogenicity evaluation except lot-to-lot consistency.

Evaluable Booster Population: All eligible randomized subjects who receive a third dose of UB-612 within the predefined window and have no major protocol deviations or protocol deviations having impact on immunogenicity data will be the Evaluable Booster Population. Evaluable Booster Population will be used to explore the immunogenicity evaluation after the booster vaccination.

Safety Population: The Safety Population (SAF) will consist of all subjects who received at least one vaccination. The Safety Set is for safety evaluation in analysis.

All safety assessments, including AEs, physical examinations (PEs), vital signs (VS), and clinical laboratory evaluations, where indicated, will be presented using descriptive statistics for each study group.

Local reactions for up to 7 days following each dose and systemic events for up to 7 days following each dose will be summarized with counts and percentages by study groups. Unsolicited AEs will be presented in counts and percentage with system organ class and preferred term by study groups. The number and percentage of MAAEs, SAEs, AESIs and ADEs will be displayed in summary table by study groups. Changes of safety laboratory measures will be summarized with descriptive statistics by study group and each time point.

The immunogenicity will be evaluated descriptively by seroconversion rate (SCR), GMT, GMFI and the associated 95% confidence intervals (CIs). **Immunogenicity evaluation for subjects received two vaccinations and three vaccinations will be summarized separately. Analysis of immunogenicity for subjects received a third dose of UB-612 will be performed with the Evaluable Booster Population only.**

For lot consistency, all pairs of lots, the two sided 95% CIs for the GMT ratios of SARS-COV-2 neutralizing titers will be calculated. If the two-sided 95% CIs for the GMTR of SARS-CoV-2 neutralizing titers are within the [0.5, 2.0] clinical limit interval, lot consistency will be concluded.

Interim Analysis:

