6.2 Primary Endpoint(s)

Immunogenicity Endpoint(s)

- Geometric mean titer (GMT) of SARS-CoV-2 neutralizing antibody on Day 57
- Seroconversion rate (SCR) of SARS-CoV-2 neutralizing antibody on Day 57

Safety Endpoint(s)

- Local reactions for up to 7 days following each dose
- Systemic events for up to 7 days following each dose
- Unsolicited AEs from Day 1 to Day 57
- MAAEs and SAEs from Day 1 to Day 365
- AESIs and ADEs from Day 1 to Day 365

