10.5.1 Analysis of Primary Safety Endpoint(s)

- Local reactions for up to 7 days following each dose

Local reactions for up to 7 days following each dose will be summarized with counts and percentages of participants with the indicated endpoint and the associated Clopper-Pearson 95% CIs by study group and each vaccination. The group comparison will be assessed by Fisher's exact test. Summary of descriptive statistics by age group will be also provided.

- Systemic events for up to 7 days following each dose

Systemic events for up to 7 days following each dose will be summarized with counts and percentages of participants with the indicated endpoint and the associated Clopper-Pearson 95% CIs by study group and each vaccination. The group comparison will be assessed by Fisher's exact test. Summary of descriptive statistics by age group will be also provided.

- Unsolicited AEs from Day 1 to Day 57

Unsolicited AEs will be presented by descriptive summary statistics (counts, percentages, and associated Clopper-Pearson 95% CIs) with system organ class and preferred term for each study group. The group comparison will be assessed by Fisher's exact test. Summary of descriptive statistics by age group will be also provided.

- MAAEs and SAEs from Day 1 to Day 365

MAAEs and SAEs will be summarized by counts, percentages, and associated Clopper-Pearson 95% CIs for each study group. The group comparison will be assessed by Fisher's exact test. Summary of descriptive statistics by age group will be also provided. **Additionally, the AESIs and ADEs occurred after third vaccination for subjects received three vaccinations will be also summarized separately.**

- AESIs and ADEs from Day 1 to Day 365

AESIs and ADEs will be summarized by counts, percentages, and associated Clopper-Pearson 95% CIs for each study group. The group comparison will be assessed by Fisher's exact test. Summary of descriptive statistics by age group will be also provided. **Additionally, the AESIs and ADEs occurred after third vaccination for subjects received three vaccinations will be also summarized separately.**

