- **Geometric mean titer (GMT) of SARS-CoV-2 neutralizing antibody and antigen-specific antibody (Anti-S1-RBD) on Day 57, Day 197 and Day 365 in adolescents**

The analysis of GMT of SARS-CoV-2 neutralizing antibody on Day 57, Day 197, 14 days post 3rd dose and Day 365 in adolescents will follow the analysis described above in GMT.

- **Seroconversion rate (SCR) of SARS-CoV-2 neutralizing antibody on Day 57 and antigen-specific antibody (Anti-S1-RBD) in adolescents**

The analysis of SCR of SARS-CoV-2 neutralizing antibody on Day 57 in adolescents will follow the analysis described above in SCR.

- **Geometric mean fold increase in SARS-CoV-2 neutralizing antibody and antigen-specific antibody (Anti-S1-RBD) on Day 57, Day 197, and Day 365 in adolescents**

The analysis of GMFI in SARS-CoV-2 neutralizing antibody and antigen-specific antibody (Anti-S1-RBD) on Day 57, Day 197, and Day 365 in adolescents will follow the analysis of secondary immunology endpoint in GMFI.

- Local reactions for up to 7 days following each dose in adolescents

The analysis of local reactions for up to 7 days following each dose in adolescents will follow the analysis of local reactions in primary safety endpoints.

- Systemic events for up to 7 days following each dose in adolescents

The analysis of systemic events for up to 7 days following each dose in adolescents will follow the analysis of systemic events in primary safety endpoints.

- Unsolicited AEs from Day 1 to Day 57 in adolescents

The analysis of unsolicited AEs from Day 1 to Day 57 in adolescents will follow the analysis of unsolicited AEs in primary safety endpoints.

- **MAAEs and SAEs from Day 1 to Day 365 in adolescents**

The analysis of MAAEs and SAEs from Day 1 to Day 365 in adolescents will follow the analysis of MAAEs and SAEs in primary safety endpoints.

- **AESIs and ADEs from Day 1 to Day 365 in adolescents**

The analysis of AESIs and ADEs from Day 1 to Day 365 in adolescents will follow the analysis of AESIs and ADEs in primary safety endpoints.

- Changes of safety laboratory measures in adolescents

The analysis of changes of safety laboratory measures in adolescents will follow the analysis of changes of safety laboratory measures in secondary safety endpoint.

- COVID-19 incidence per 1000 person-years of follow-up based on PCR test

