10.9 Interim Analysis

Six interim analyses and reports will be performed when (1) adult immunogenicity data (350 evaluable young adults and 154 evaluable elderly subjects) for Day 57 are available; (2) at least half of core group subjects (at least 3500 evaluable subjects) will be completed Day 85 safety follow up, as EUA application dossier; (3) all immunogenicity data for lot-to lot consistency of Day 57 are available, EUA application dossier; (4) 350 evaluable adolescents completed Day 57 safety follow up, as supplementary dossier for EUA; **(5) immunogenicity and safety data for young and elderly adult subjects receiving 3rd vaccination completed Visit 7, which is 14 days after 3rd vaccination; (6) immunogenicity and safety data for adolescent subjects receiving 3rd vaccination completed Visit 7, which is 14 days after 3rd vaccination.**

The first four analyses and reports will be analysed and drafted by the unblinded statistician, reviewed by the IDMC, and submitted to appropriate regulatory authorities for review if as EUA application dossier or supplementary dossier for EUA.

For the evaluation of safety, immunogenicity, and lot-to-lot consistency, the following endpoints will be included in the first four interim analyses.

- Local reactions, systemic events, unsolicited AEs, and SAEs
- Changes of safety laboratory measures
- Changes of vital signs and physical examinations
- Seroconversion rate of SARS-CoV-2 neutralizing antibody and antigen-specific antibody (Anti-S1-RBD) on Day 57
- Geometric mean titer of SARS-CoV-2 neutralizing antibody and antigen-specific antibody (Anti-S1-RBD) on Day 57
- Geometric mean fold increase in SARS-CoV-2 neutralizing antibody and antigen-specific antibody (Anti-S1-RBD) on Day 57
- Lot consistency by the comparisons of the GMT of SARS-CoV-2 neutralizing titers on Day 57 induced by 3 independent UB-612 vaccine clinical materials. The 95% confidence intervals between groups will be within the margin of 0.5 to 2.

For last two interim analyses (i.e., interim analysis (5) and (6)), the analyses demonstrate the immunogenicity and safety data on the adult and adolescent subjects received 3rd dose of UB-612 including (but not limited to) following endpoints.

- **Local reactions, systemic events, unsolicited AEs, and SAEs after 3rd dose of UB-612**
- **Changes of safety laboratory measures**
- **Changes of vital signs and physical examinations pre/post 3rd dose of UB-612**

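### V-205: the post-third-dose rule under the MAAE/SAE primary safety endpoint names AESIs and ADEs, so the final analysis orders no separate summary of MAAEs and SAEs after dose 3

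*Supplement*

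**What the plan says.** All references are to the V-205 protocol.

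- **Endpoint.** Section 6.2 lists "MAAEs and SAEs from Day 1 to Day 365" among the primary safety endpoints. AESIs and ADEs over the same window are a separate entry.
- **Main analysis.** Section 10.5.1 states: "MAAEs and SAEs will be summarized by counts, percentages, and associated Clopper-Pearson 95% CIs for each study group". Groups are compared by Fisher's exact test.
- **Third-dose rule.** The same bullet closes with "Additionally, the AESIs and ADEs occurred after third vaccination for subjects received three vaccinations will be also summarized separately". The following bullet, on AESIs and ADEs, closes with the identical sentence.
- **Split by dose elsewhere.** In section 10.5.1 only local reactions and systemic events are given with "Clopper-Pearson 95% CIs by study group and each vaccination".
- **Synopsis.** For these events: "The number and percentage of MAAEs, SAEs, AESIs and ADEs will be displayed in summary table by study groups". Two and three doses are kept apart for antibody results only: "Immunogenicity evaluation for subjects received two vaccinations and three vaccinations will be summarized separately".
- **Interim analyses 5 and 6.** Section 10.9 lists "Local reactions, systemic events, unsolicited AEs, and SAEs after 3rd dose of UB-612", for subjects who have completed Visit 7, 14 days after dose 3.
- **Adolescents.** Section 10.7 says that their MAAE and SAE analysis "will follow the analysis of MAAEs and SAEs in primary safety endpoints".

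**The concern.** The sentence fits the AESI/ADE bullet and appears to have been carried into the MAAE/SAE bullet without changing the event types. Its position shows that a post-dose-3 summary was meant for MAAEs and SAEs, but its wording does not produce one.

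This matters because of the design after Day 197. Placebo recipients are unblinded and leave at Visit 5 (sections 7.1 and 8.1.8), and dose 3 goes only to vaccine recipients who agree to it (section 8.1.9). There is no concurrent randomised control after dose 3, so a tabulation restricted to that period is the natural way to see which serious and medically attended events followed the booster. Without it, those events enter one Day 1 to 365 percentage for the vaccine arm, mixed with events after one or two doses. A programmer who followed the text would produce one table twice and omit another.

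**Working it through.** No sample size, power or error rate is at issue. The check is a reading of every V-205 safety-analysis provision, plus calendar arithmetic.

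**1. Does any other provision separate MAAEs or SAEs after dose 3 in the final analysis?**

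| Place | What it provides | Post-dose-3 split of MAAEs/SAEs? |
|---|---|---|
| Synopsis, statistical analysis | MAAE, SAE, AESI and ADE table by study group | No |
| 10.3 | Safety Population: anyone with at least one vaccination. The Evaluable Booster Population serves immunogenicity | No boosted safety set |
| 10.5 | Separate summaries by category (SAEs, related unsolicited AEs); by-subject listings | No; by category, not dose |
| 10.5.1, MAAE/SAE bullet | Pooled summary, then the rule naming AESIs and ADEs | No, as worded |
| 10.5.1, AESI/ADE bullet | The same rule, where it fits | Only for events that are also AESIs or ADEs |
| 10.7, adolescents | Refers back to 10.5.1 | Inherits the error |
| 10.9, interims 5 and 6 | SAEs and unsolicited AEs after dose 3, at Visit 7 | Interim only, to 14 days |

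None supplies the missing summary.

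**2. How much follow-up does this concern?**

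Inputs: dose 3 at Day 197 to 242 (section 8.1.9); window Day 1 to Day 365 (section 6.2); Visit 7 at 14 days after dose 3 (section 8.1.11).

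- Window length: 365 − 1 = 364 days.
- Dose 3 on Day 197: 365 − 197 = 168 days remain; 168/364 = 46%.
- Dose 3 on Day 242: 365 − 242 = 123 days remain; 123/364 = 34%.
- Beyond Visit 7: 168 − 14 = 154 days, or 123 − 14 = 109 days.

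The last visit may move by 45 days either way (section 8.1.13). The extremes are therefore 410 − 197 = 213 days and 320 − 242 = 78 days after dose 3.

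These are shares of a boosted subject's nominal calendar time. The protocol gives neither the expected number of boosted subjects nor MAAE or SAE rates, so the number of events affected cannot be derived.

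**The case against.** The case against rests on five points.

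1. **It is an evident misprint.** The heading of the bullet shows what was intended. This stands: the point is a drafting error, not a deliberate analysis choice. It still needs correcting, because the literal instruction is the wrong one and sits under a primary safety endpoint.
2. **The SAP may put it right.** Section 10.1 leaves full analysis details to a SAP, and none for V-205 is shown. A reader might infer that MAAEs and SAEs after dose 3 will never be separated. The documents do not support that; they show only that the protocol's own text does not order it. The fault is a wrong instruction in the protocol, not a detail left to the SAP, and a SAP that followed it would repeat it.
3. **Interims 5 and 6 cover part of the gap.** Their endpoint list is expressly open-ended and includes unsolicited AEs, which can contain MAAEs (defined in section 9.5.6.4) without that label. So it would be wrong to say that every MAAE after dose 3 goes unsummarised. That cover ends at Visit 7.
4. **Other outputs overlap.** An SAE or MAAE that is also an AESI or ADE reaches the separate post-dose-3 summary, and the listings allow a manual split. No data are lost, but neither output replaces a planned summary of all MAAEs and SAEs.
5. **The stakes can be exaggerated.** A reader might infer that two-dose safety as a whole is contaminated. The first four interims report unsolicited AEs and SAEs at Day 57 or Day 85 milestones, well before dose 3 at Day 197 or later, so early two-dose safety is reported on its own. A reader might also infer that a separate table is the only way to judge dose 3. Vaccine recipients who decline it are still followed to 12 months and offer a concurrent, though non-randomised, reference. The pooling concerns the later part of the window.

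**Conclusion.** The point holds as a drafting error with a real, limited consequence. As written, the V-205 final analysis summarises AESIs and ADEs after dose 3 twice. MAAEs and SAEs after dose 3 that are not also AESIs or ADEs appear only in the pooled Day 1 to 365 vaccine-arm figures. The follow-up concerned is 123 to 168 nominal days per boosted subject, of which only the first 14 are covered, in part, by interims 5 and 6.

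This rests on the protocol text alone, on nominal visit days, and on no unseen SAP having restored the split. It implies nothing about the size of any safety signal or the degree to which one would be diluted.

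**What to change.** - In section 10.5.1, in the last sentence of the MAAE/SAE bullet, replace AESIs and ADEs with MAAEs and SAEs. State that the denominator is subjects who received three vaccinations. Leave the AESI/ADE bullet as it is.
- Keep the Day 1 to 365 table, since that is how section 6.2 defines the endpoint. A supplementary table censoring boosted subjects at dose 3 would give a cleaner two-dose summary, but it is optional and goes beyond correcting the sentence.
- The adolescent analysis in section 10.7 needs no edit of its own, because it refers back to this text.

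The cost is one corrected sentence and one extra summary table. No new data are needed: section 8.1.13 already has AESIs, MAAEs and SAEs recorded at Day 365.

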10.5.2 Analysis of Secondary Safety Endpoint

- Changes of safety laboratory measures

Changes of safety laboratory measures will be summarized with descriptive statistics by study group and time point. ANCOVA model with laboratory baseline values as covariate will analyse changes of safety laboratory measures for testing the difference between study groups. Intra-group difference in safety laboratory measures will also be analysed by paired t test. Summary of descriptive statistics by age group will be also performed.

10.6 Immunogenicity Evaluation

10.6.1 Analysis of Primary Immunogenicity Endpoint(s)

- Geometric mean titer (GMT) of SARS-CoV-2 neutralizing antibody on Day 57

For SARS-CoV-2 neutralizing antibody, GMT and 2-sided 95% CIs will be provided for each study group. Additionally, the difference between UB-612 vaccine and placebo groups will be analysed by ANCOVA model under log-transform data with baseline level as covariate and effect of study treatment, if appropriate. Summary of descriptive statistics by age group will be also performed.

- Seroconversion rate (SCR) of SARS-CoV-2 neutralizing antibody on Day 57

The SCR will be presented as count and percentage in frequency table, and the 95% exact (Clopper-Pearson) confidence interval will be provided as well by study group. Fisher's exact test will be used for the comparison of UB-612 vaccine group and placebo group. Summary of descriptive statistics by age group will be also performed.

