10.5 Immunogenicity Evaluation

10.5.1 Analysis of Immunogenicity Endpoints

- Geometric mean titer (GMT) of antigen-specific antibody (Anti-S1-RBD) on Day 14, 28, 42, 56, 112, and 196.
GMT of antigen-specific antibody of antigen-specific antibody (Anti-S1-RBD) on Day 14, 28, 42, 56, 112, and 196 will be described by descriptive statistics and the 95% confidence interval for study vaccine group. Additionally, the difference among vaccine groups will be analyzed by ANCOVA model under log-transform data with baseline level as covariate, if appropriate. Pair-wise comparisons of least square means from the ANCOVA model will be presented. The reverse cumulative distribution plot will be provided to display the distribution of the GMT of Anti-S1-RBD by time points for each vaccine group.
- Seroconversion rate (SCR) of antigen-specific antibody (Anti-S1-RBD) on Day 14, 28, 42, 56, 112, and 196.
The SCR will be presented as count and percentage in frequency table, and the 95% exact (Clopper-Pearson) confidence interval will be provided as well. The group comparison among dose groups will be assessed by Fisher's exact test.
- Geometric mean fold increase of antigen-specific antibody (Anti-S1-RBD) on Day 14, 28, 42, 56, 112, and 196.
The geometric mean fold increase (GMI) in each study vaccine group is summarized by descriptive statistics and the 95% confidence interval for study vaccine group. The difference among vaccine groups will be analysed by ANOVA. Pair-wise comparisons of least square means from the ANOVA model will be presented. The reverse cumulative distribution plot will be provided to display the distribution of the GMI of Anti-S1-RBD by time points for each vaccine group.

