3. Unsolicited adverse events were reported by 85.0% subjects in UB-612 vaccine 10 µg group, 60.0% subjects in UB-612 vaccine 30 µg group, and 35.0% subjects in UB-612 vaccine 100 µg group. Most of unsolicited adverse events was judged as Grade 1 and 2. Blood pressure diastolic increased in 2 subjects and blood pressure ambulatory increased in 1 subject in UB-612 vaccine 10 µg group, and blood pressure diastolic increased in 1 subject in UB-612 vaccine 30 µg group, were reported as Grade 3. No \geq Grade 3 unsolicited adverse events was found in UB-612 vaccine 100 µg group.
4. Due to procedural issues, some local reactions at the vaccination sites were recorded in the AE eCRF as unsolicited events and were not reported in the subject e-diary as solicited events. The related-vaccine unsolicited AEs were found in 50.0%, 15.0%, and 5.0% subjects in UB-612 vaccine 10, 30 and 100 µg group, respectively. The frequently related unsolicited adverse events related to vaccine were injection site reaction (6 subjects, 30.0%) and malaise (5 subjects, 25.0%) in UB-612 vaccine 10 µg group. The injection site rash, alanine

aminotransferase increased, haemoglobin decreased, which were reported as the related unsolicited adverse events in each 1 subjects in UB-612 vaccine 30 µg group. Constipation in 1 subjects was judged as related unsolicited adverse events in UB-612 vaccine 100 µg group.

5. No deaths, and no serious adverse events reported was found in this study till now. No clinically significant change in the physical examination or ECG measurement in this trial was noted.

The immune responses in antigen-specific antibody and neutralizing antibody could be observed at Day 28 and could achieve 4-fold increase in the majority of 10, 30, and 100 µg vaccine group at Day 42 and 56.

1. All subjects in UB-612 vaccine 10, 30 and 100 µg group revealed no detection in antigen-specific antibody before vaccination. In UB-612 vaccine 10 µg group, GMT increased to 350.79 at Day 42 (14 days after second vaccination) and 526.98 at Day 56 (28 days after second vaccination). In UB-612 vaccine 30 µg group, GMT increased to 366.80 at Day 42 and 269.06 at Day 56. In UB-612 vaccine 100 µg group, GMT increased to 2240.15 at Day 42 and 805.11 at Day 56.

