7 INVESTIGATIONAL PLAN

7.1 Overall Study Design and Plan: Description

This is a phase II, observer-blind, multiple-centre, randomized, placebo-controlled study to evaluate the immunogenicity, safety, tolerability and lot consistency of 2 doses of UB-612 vaccine in adolescent, younger and elderly adults. Around 3850 adult subjects will be randomized to be composed of the core group for EUA application, while around 385 adolescents will be randomized to be the supplementary group for broader indication. All subjects will be randomly allocated to receive 2 doses of 100 µg vaccine or placebo in a 6:1 ratio, including 462 aged from >18 to < 65 years old, evaluable subjects in the lot-to-lot consistency group. As for immunogenicity, at least 350 evaluable young **adults** (aged >18 to < 65 years old) and 154 evaluable elderly (aged ≥ 65 years old) will be enrolled for descriptive analysis. Subjects in immunogenicity group should be enrolled first. All subjects will be included in the safety group, and it is intended that a minimum of 770 subjects will be randomized to be in the ≥ 65-year stratum. Adolescents will start to enrol after recruitment of the core group has been completed. Around 385 adolescents will be randomized to be allocated in 6:1 ratio, in which 154 evaluable adolescents will have immunogenicity data to compare with adults.

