7.4.6 Method of Assigning Subjects to Treatment Groups

The study vaccine and placebo will be randomly assigned to subjects. The randomized sequence of study treatments will be generated by an independent qualified biostatistician. The randomization schedule will be kept and maintained by the designated personnel before the study begins and until the database lock. The independent biostatistician prepares the randomization schedules via the SAS software (9.4 or higher version).

For core group, around 3850 participants will be randomly assigned to UB-612 vaccine 100 µg or placebo with a 6:1 randomization ratio (vaccine: placebo) by block randomization. In addition, a total of 966 evaluable subjects including 812 evaluable young adult and 154 evaluable elderly subjects from core group will be apportioned to immunogenicity and **lot-to-lot group** with a randomization ratio of 6:1 to UB-612 vaccine (696 evaluable young adult subjects and 132 evaluable elderly subjects) and placebo (116 evaluable young adult subjects and 22 evaluable elderly subjects). Furthermore, the 396 evaluable young adult subjects in immunogenicity group assigned to UB-612 vaccine will be allocated to 3 specified vaccine lots with a 1:1:1 ratio for evaluating the lot-to-lot consistency. Therefore, a total of 462 evaluable young adult subjects of immunogenicity group will be randomized to 3 vaccine lots and placebo with a ratio of 2:2:2:1 (vaccine lot 1: vaccine lot 2: vaccine lot 3: placebo).

In supplementary group, around 385 adolescent subjects aged from 12 to 18 years old will randomly receive UB-612 vaccine 100 µg or placebo with allocation rate 6:1, too.

Eligible subjects will receive a random number at randomization in form of a sealed envelope. The authorized unblinded dispenser(s)/administrator(s) who involve in the treatment of vaccine/placebo will be required to open the envelope and administer the corresponding treatment assigned by the envelope. For any reason that a subject withdraws from the study prematurely after the randomization, his/her randomization number will not be reused. The next eligible subject will receive the lowest available randomization number.

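### The V-205 GMT models adjust only for a baseline titre that will probably be nearly constant and omit age class, by which vaccine and placebo numbers are set; adding it narrows the intervals modestly

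*Supplement*

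**What the plan says.** V-205 section 10.6.1 gives the primary GMT model in full: the arms are to be "analysed by ANCOVA model under log-transform data with baseline level as covariate and effect of study treatment", with the qualifier that this is done if appropriate. Section 10.6.2 uses the same model for the later neutralizing GMTs and for anti-S1-RBD. GMFI is compared by a t test on the log scale and SCR by Fisher's exact test. For each of these endpoints, age group appears only as a further descriptive summary.

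Age is nevertheless part of the design. Section 7.1 states that "it is intended that a minimum of 770 subjects will be randomized to be in the ≥ 65-year stratum". Section 7.4.6 fixes the vaccine arm of the immunogenicity and lot-to-lot group at "696 evaluable young adult subjects and 132 evaluable elderly subjects", with 116 and 22 on placebo. That section speaks of block randomization but names no stratification factor, so age-stratified blocks are implied, not stated.

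On the covariate, V-123 section 5.5 reports that the V-122 subjects in all three dose groups "revealed no detection in antigen-specific antibody before vaccination", and says the same of neutralizing antibody. Table 5-1 there gives Day 0 GMTs of 10.00 (ELISA) and 2.50 (neutralizing) in every group of 20, with no confidence interval. V-122 section 9.6.6.1 shows that 10 is the value imputed for any ELISA titre below 20.

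**The concern.** A covariate helps only if it varies and predicts the outcome. In V-122 baseline titre did not vary at all, so a slope on it could not be estimated. V-205 excludes previous exposure to SARS-CoV-2 (section 7.4.3), so its baselines should also sit mostly at the floor. The one adjustment that the V-205 model names may therefore do almost nothing.

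Age class is known before vaccination, is a design factor, and may well relate to titre, yet it is left out of the comparison. Any difference between young and elderly titres then stays in the residual error. What is at stake is the width of the interval around the primary GMT ratio, and agreement between the analysis and the design.

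**Working it through.** **Inputs**
- Evaluable numbers: 812 young adults, 154 elderly, 966 in total (V-205 section 7.4.6).
- Planning SD of log10 titre: 0.6 (V-205 section 10.2.2).
- V-122 100 µg Day 56 neutralizing GMT 102.97, 95% CI 70.764 to 149.836, n = 20 (V-123 Table 5-1).
- Elderly GMT relative to young: given nowhere in the documents. Assumed to be 1/2 to 1/3, that is d = 0.301 to 0.477 log10.

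**1. Allocation reproduced.** 812 × 6/7 = 696 and 812/7 = 116; 154 × 6/7 = 132 and 154/7 = 22. All four match. The placebo share is 1/7 in each class, so treatment and age class are uncorrelated, and adding age leaves the treatment estimate unchanged.

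**2. Constant baseline.** If every baseline value is equal, the columns for intercept, treatment and baseline have rank 2, the same as intercept and treatment alone. The ANCOVA is then a two-sample t test with identical estimate and standard error.

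**3. SD from V-122.** SD = [log10(upper/lower)/2] ÷ [t(0.975, n−1)/√n].
- Check on the 10 µg group (24.020 to 73.146): 0.2418/0.4680 = 0.517; V-205 section 10.2.2 prints 0.52.
- 100 µg group: 0.1629/0.4680 = 0.348.

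**4. Cost of omitting age.** The elderly share is p = 154/966 = 0.159, so p(1−p) = 0.134. The ratio of unadjusted to adjusted residual SD is √(1 + p(1−p)d²/SD²).

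| SD | d | ratio | fall in SD from adding age |
|---|---|---|---|
| 0.6 | 0.301 | 1.017 | 2% |
| 0.6 | 0.477 | 1.042 | 4% |
| 0.348 | 0.301 | 1.049 | 5% |
| 0.348 | 0.477 | 1.119 | 11% |

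**5. Check with placebo at the floor.** The formula gives both arms the same age effect. As a check, 966 subjects were simulated at the planned numbers, with placebo fixed at log10(2.5), vaccinees centred on log10(102.97), and the elderly deficit in vaccinees only. The SE of the treatment difference, without and with the age term, was:

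| SD | d | without age | with age |
|---|---|---|---|
| 0.6 | 0.3 | 0.0519 | 0.0511 |
| 0.6 | 0.5 | 0.0534 | 0.0513 |
| 0.35 | 0.3 | 0.0311 | 0.0299 |
| 0.35 | 0.5 | 0.0336 | 0.0304 |

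These are falls of about 1.5%, 4%, 4% and 10%, in line with step 4. The treatment difference was 1.53 to 1.57 log10 in these four cases, between 29 and 50 standard errors.

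**The case against.** The case against rests on five arguments.

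- **The SAP may add age.** V-205 section 10.1 leaves full detail to an SAP that is not shown. This stands in part. However, the protocol does write out the model terms, and section 10.8 defers only further populations and subgroups.
- **The model applies only if appropriate.** The qualifier lets the analyst drop the ANCOVA when baseline is constant, and nothing would then be invalid. That is right, but no replacement model is named.
- **V-205 baselines may vary.** Unlike V-122, V-205 requires no negative serology or PCR at entry, so some baselines may lie above the floor. This stands, and it is a reason to keep baseline titre in the model.
- **The result would not change.** This stands. The contrast is far too large for age to matter to the test, and the synopsis describes the immunogenicity evaluation as descriptive. The one powered immunogenicity test, lot consistency, is already confined to ages above 18 and below 65.
- **The assumed elderly deficit has no source here.** This stands. The synopsis remark on immune senescence concerns variability, not a lower mean, and an age intercept would not correct unequal variances.

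A reader might go further and infer that the V-122 dose comparisons are biased, since those groups were filled in sequence and their model, "analyzed by ANCOVA model under log-transform data with baseline level as covariate, if appropriate", had a constant covariate. The documents do not show this. With an assumed age SD of 10 years and an assumed slope of 0.01 log10 per year, a one-SE chance imbalance is 10 × √(2/20) = 3.2 years, a factor of 10^0.032 = 1.07. That is chance variation resting on two unsupported assumptions. For comparison, the one-SE factor on the Day 56 neutralizing ratio of 100 to 30 µg is 10^√((0.348² + 0.387²)/20) = 1.31, against an observed ratio of 102.97/28.99 = 3.55. V-122 titres had also been summarized already, so changing that model now would be post hoc.

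**Conclusion.** The point holds for V-205 as a small, nearly free gain in efficiency. The written GMT model has one covariate, which will probably be close to constant, and it omits the age class by which vaccine and placebo numbers are set.

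A reader might infer that the omission biases the treatment effect or threatens the primary conclusion. It does neither: the 6:1 ratio holds in both classes, and the expected contrast is tens of standard errors from zero. Nor do the documents show that baseline adjustment will be wholly idle in V-205, because seronegativity is not an entry condition.

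The size depends on an elderly GMT of one half to one third of the young GMT, which is an assumption. The SD of 0.35 comes from 20 V-122 subjects from a trial limited to ages 20 to 55; the protocol's own 0.6 gives the smaller gain.

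**What to change.** In V-205 sections 10.6.1 and 10.6.2, or in the SAP before unblinded data are analysed:

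- Keep baseline titre and add age stratum (above 18 to below 65; 65 and over) as a factor in the adult GMT models.
- For GMFI, replace the two-sample t test by a linear model on the log scale with treatment and age stratum.
- Optionally, use a stratum-adjusted comparison for SCR, such as Mantel-Haenszel. Little change is expected if placebo seroconversion is near zero.
- State in section 7.4.6 whether the randomization blocks are stratified by age.

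The cost is a few words and one degree of freedom out of 966 evaluable subjects. Age is already collected, and the descriptive summaries by age group stay as they are. No change to V-122 is proposed.
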